A contrast enhanced CT scan of the neck, chest, abdomen and pelvis will be performed at cycles 3, 6 and 8 of treatment to assess response during treatment. If the patient has not progressed after 8 cycles they will continue to be followed up with CT scans at 12, 16 and 20 months from treatment start or sooner if the Investigator is concerned there may be disease progression or if the patient discontinues treatment. After 20 months from treatment start, radiological follow-up will be as per local standard with data collected every 6 months.

Patients will continue to be followed up for progression and survival until the end of trial.

Trials Office Contact Details

AVAIL-T trial team
Centre for Clinical Haematology
Queen Elizabeth Hospital
[name]
[contact]
[contact]
Email: [contact]

ABBREVIATIONS

ABPI	ASSOCIATION OF THE BRITISH PHARMACEUTICAL INDUSTRY
ACTH	ADRENOCORTICOTROPIC HORMONE
ADCC	ANTIBODY DEPENDENT CELLULAR CYOTOXICITY
ADL	ACTIVITIES OF DAILY LIVING
AE	ADVERSE EVENT
AHA	AMERICAN HEART ASSOCIATION
AIDS	ACQUIRED IMMUNODEFICIENCY SYNDROME
AITL	ANGIOIMMUNOBLASTIC LYMPHOMA
ALCL	ANAPLASTIC LARGE CELL LYMPHOMA
ALP	ALKALINE PHOSPHATASE
ALT	ALANINE TRANSAMINASE
AML	ACUTE MYELOID LEUKEMIA
ANC	ABSOLUTE NEUTROPHIL COUNT
AR	ADVERSE REACTION
AST	ASPARTATE TRANSAMINASE
CR	COMPLETE REMISSION/RESPONSE
CrCL	CREATININE CLEARANCE
CRCTU	CANCER RESEARCH UK CLINICAL TRIALS UNIT (UNIVERSITY OF BIRMINGHAM)
CRF	CASE REPORT FORM
CRP	C-REACTIVE PROTEIN
CR UK	CANCER RESEARCH UK
CT	COMPUTER TOMOGRAPHY
CTC	COMMON TERMINOLOGY CRITERIA
CTCAE	COMMON TERMINOLOGY CRITERIA FOR ADVERSE EVENTS
CTCL	CUTANEOUS T-CELL LYMPHOMA
CV	CURRICULUM VITAE
DCF	DATA CLARIFICATION FORM
DNA	DEOXYRIBOSE NUCLEIC ACID
EATL	ENTEROPATHY ASSOCIATED T-CELL LYMPHOMA
ECG	ELECTROCARDIOGRAM
ECMC	EXPERIMENTAL CANCER MEDICINE CENTRE
ECOG	EASTERN COOPERATIVE ONCOLOGY GROUP
EDC	ELECTRONIC DATA CAPTURE
EMEA	EUROPEAN MEDICINES AGENCY
ENKL	EXTRANODAL NK/T- CELL LYMPHOMA
EORTC	EUROPEAN ORGANISATION FOR RESEARCH AND TREATMENT OF CANCER
ESC	EUROPEAN SOCIETY OF CARDIOLOGY
FBC	FULL BLOOD COUNT
FDA	(USA) FOOD AND DRUG ADMINISTRATION
FSH	FOLLICLE-STIMULATING HORMONE
GCP	GOOD CLINICAL PRACTICE

GGT	GAMMA-GLUTAMYL TRANSPEPTIDASE
GMP	GOOD MANUFACTURING PRACTICE
GP	GENERAL PRACTITIONER
HBV	HEPATITIS B VIRUS
HCG	HUMAN CHORIONIC GONADOTROPHIN
HCV	HEPATITIS C VIRUS
HGB	HAEMAGLOBIN
HIV	HUMAN IMMUNODEFICIENCY VIRUS
IB	INVESTIGATOR BROCHURE
ICF	INFORMED CONSENT FORM
ICOS	INDUCIBLE CO-STIMULATOR

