7.2 Treatment Schedule

Avelumab 10 mg/kg will be administered once every 14 days for a proposed duration of 8 cycles (28 day cycles), (16 doses).

If the patient is showing clinical benefit following 8 cycles of trial treatment patients may continue to receive avelumab treatment at the treating Investigator's discretion, until loss of response, toxicity, or death.

Every effort should be made for patients to attend on the scheduled visit days. However, if a patient is unable to attend on the specified day, assessments may be scheduled for +/- 3 days.

The full blood count should be assessed prior to each treatment (within 24 hours of treatment) to ensure the following criteria are met:

- Platelets $> 75 \times 10^9/L$
- Neutrophils $> 1.0 \times 10^9/L$
- Bilirubin $< 1.5 \times ULN$
- Creatinine clearance (CrCL) (Cockcroft-Gault) $\geq 30 \text{ ml/min}$.
- ALT/AST $\leq 1.5 \times ULN$ on Cycle 1 day1; thereafter $\leq 3 \times ULN$

Please also refer to Section 7.5 for dose delays and modifications, and to section 7.7 for concomitant medications.

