1 If baseline showed involvement, a further biopsy is required at radiological CR to confirm CR. Further bone marrow biopsy should also be performed if progression within the marrow is suspected and the CT does not show progression.

2 Haematology – Full blood count (Haemoglobin, Platelets, WBC, Neutrophils and Lymphocytes)

3 Blood Chemistry – Standard blood chemistry (to include bilirubin, GGT, AST/ALT, Alkaline phosphate, Calcium (adjusted), Creatinine, CRP, Magnesium, Phosphate, Potassium, Sodium, and glucose –non fasted)

4 Triglycerides and cholesterol at baseline, Cycle 4 days 1 and End of Treatment only

5 To be performed before and after avelumab infusion

6 CT scans to be performed within the time period after the day 15 dose and prior to next day 1 dose.

7 Post 8 cycles CT scans and research bloods will be performed in line with the follow-up schedule

8 End of Treatment scan only required if treatment stopped early and no scan has been conducted in the previous 28 days. Progression scan upon suspected progression outside of scheduled scans.

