7.3.4 Physical examination/clinical disease assessment

Patients will receive a physical exam, including vital signs (blood pressure, pulse, oxygen saturation, weight and height (baseline only)), and assessment of ECOG performance status on day 1 of each cycle and at the End of Treatment visit. The physical exam should also include investigation of skin lymphoma deposits and rashes, liver and spleen assessment and assessment of lymph node measurements.

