7.3.5 Radiological Assessment – CT scans

A contrast enhanced CT scan of the neck, chest, abdomen and pelvis will be performed at cycles 3, 6 and 8 of treatment to assess response during treatment. If the patient discontinues treatment early an End of treatment scan should be performed, if a scan has not been conducted with the last 28 days. Scans should be reported with two dimensional measurements of each lesion in millimetres (mm) if measureable.

Immunotherapeutic agents such as avelumab may produce antitumor effects by potentiating endogenous cancer-specific immune responses. The response patterns seen with such an approach may extend beyond the typical time course of responses seen with cytotoxic agents, and can manifest as a clinical response after an initial increase (pseudo-progression) in disease burden. The Investigator's judgment of radiological response on early CT scans should be based on the overall benefit-risk assessment and the patient's clinical condition, including performance status, clinical symptoms, adverse events and laboratory data.

If the patient has not progressed after 8 cycles they will continue to be followed up with CT scans at 12, 16 and 20 months from treatment start or sooner if the investigator is concerned there may be disease progression. After 20 months from treatment start radiological follow-up will be as per local standard with data collected every 6 months.

Response will be assessed according to the Revised Response Criteria for malignant lymphoma²⁷ (appendix 1).

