7.9 Patient Follow Up

All patients will need to be followed up for safety (AEs) up to 30 days (+/- 5 days) after the last dose of avelumab and for disease progression / survival until the end of the trial (minimum of 12 months follow-up from the date of commencing treatment for the last patient).

If the patient stops trial treatment but has not progressed, they will be reviewed with a CT scan of neck, chest, abdomen and pelvis at 8, 12, 16 and 20 months or on clinical suspicion of progression (whichever is sooner).

If there is no evidence of progression after 20 months, patients will have no specific trial follow up, but their referring physician may be contacted every 6 months to determine progression and survival data.

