12.1.2 Secondary outcome measures

- Toxicity assessed using CTCAE v4.0 will be defined as the number and proportion of patients who experience one or more grade 3 or 4 adverse event or serious adverse event of any grade
- Best overall response (Partial Remission (PR) + Complete Response (CR)) at any time of treatment will be assessed using contrast-enhanced CT scans of the neck, chest, abdomen and pelvis, using the Revised Response Criteria for Malignant Lymphoma (²⁷)
- Maximum percentage change in the sum of the product of diameters (SPD) of target tumour masses assessed by contrast-enhanced CT scans of the neck, chest, abdomen and pelvis, using the Revised Response Criteria for Malignant Lymphoma²⁷
- Duration of response is defined as the time from first documented response until relapse/progression, as determined by the Revised Response Criteria²⁷, or death. Patients who are relapse/progression free and alive will be censored at date last seen.
- Progression free survival is defined as the time from date of registration to the date of disease progression or date of death from any cause. Patients not reaching progression or death at the time of analysis will be censored at the last date they were known to be alive and progression free. Patients will be followed up for a minimum of 12 months.
- Overall survival time is defined as the time from date of registration to the date of death from any cause. Patients discontinuing the study, lost to follow-up or still alive at the end of the study will be censored at the date of last follow-up. Patients will be followed up for a minimum of 12 months.

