12.2 Analysis of Outcome Measures

Primary Outcome Measures

- Best overall response rate (PR + CR) during 8 cycles of treatment will be presented as the number and proportion of patients achieving a response over the total number of patients registered to the trial. Patients who die due to disease or toxicity during the first 8 cycles of treatment and patients who are not assessable will be classed as non-responders.

Posterior probability plots will also be produced together with the probability that the true effect is greater than 35%.

Secondary Outcome Measures

- Toxicity - The number and proportion of patients who experience one or more grade 3 or 4 adverse event or serious adverse event of any grade will be reported over the total number patients in the trial

- Time to event outcomes will be estimated using Kaplan Meier method. Point estimates will be presented at 6 and 12 months with 95% confidence intervals.
- Reduction in tumour size measured as maximum percentage change in the radiological sum of the product of the diameters from baseline will be presented as a mean and standard deviation or medians with an interquartile range depending on the distribution of the data.

Exploratory outcome measures

- Percentage of PD-L1 expression will be analyses at the Leicester Cancer Centre
- Cell free DNA levels and disease status correlation will be performed by the Leicester Cancer Centre
- Multicolour peripheral blood immunophenotyping will be performed by the Leicester Cancer Centre
- CyTOF study: biomarkers of response data will be acquired via mass flow cytometry at the Leicester Cancer Centre

All summaries and statistical analyses will be performed on an intention-to-treat (ITT) population including patients who are ineligible or non-compliant and a per protocol population of only patients who were eligible and received at least 1 dose of treatment.

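### 12-month PFS is read just before the 12-month CT, after 4 to 5 months without a scheduled scan, so it can only err upward; the effect is modest and cheap to address

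*Combined protocol and SAP*

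**What the plan says.** Two clocks are in use.

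- **PFS clock.** Section 12.1.2: "Progression free survival is defined as the time from date of registration to the date of disease progression" or death. Section 12.2 applies Kaplan-Meier and says "Point estimates will be presented at 6 and 12 months with 95% confidence intervals".
- **Scan clock.** CTs on treatment fall in cycles 3, 6 and 8, each between the day 15 dose and the next day 1 (Table 2, footnote 6). Section 7.3.5 then has patients without progression "followed up with CT scans at 12, 16 and 20 months from treatment start". Patients who stay on avelumab beyond cycle 8 get no additional scheduled scans: "Post 8 cycles CT scans and research bloods will be performed in line with the follow-up schedule" (Table 2, footnote 7). For patients who stop without progression, section 7.9 says "they will be reviewed with a CT scan of neck, chest, abdomen and pelvis at 8, 12, 16 and 20 months", without naming an origin for those months.

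Treatment follows registration (Trial Synopsis, Trial Duration). I found no limit on the gap between them, no rule for dating a progression that arose between scans, and no interval-censored analysis.

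The plan also provides for detection between scheduled scans. The synopsis allows a CT "or sooner if the Investigator is concerned there may be disease progression or if the patient discontinues treatment". Section 7.3.4 requires an examination on day 1 of every cycle: "The physical exam should also include investigation of skin lymphoma deposits and rashes, liver and spleen assessment and assessment of lymph node measurements".

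**The concern.** A progression first seen on a scan is dated at or after its onset, never before. A Kaplan-Meier curve is therefore highest, relative to the truth, just before a scan that follows a long interval without one. The 12-month landmark sits at such a point for two reasons: the scan clock starts later than the PFS clock, and the landmark is placed at a scan visit. Patients who progressed silently between about month 7 or 8 and month 12 are then counted as progression-free at 12 months.

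Twelve-month PFS is one of only two planned PFS landmarks. The trial has a single arm, so no comparator shares the shift and offsets it. At stake is a secondary result that reads somewhat too well when a larger trial is being considered.

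**Working it through.** **The plan's own figures.** The plan states no expected PFS, event count or PFS precision, so there is no PFS figure to reproduce. Its only sizing figures concern response: 60% and 84% probability of a rate above 35% for 11 and 13 responses in 30. Under a uniform beta prior these come out at 60.3% and 84.1%.

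**Calendar (1 month = 30.44 days, from treatment start).**

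- The cycle 8 CT falls 210 to 224 days after treatment start, i.e. 6.9 to 7.4 months.
- Interval to the 12-month CT: 365.25 − 224 = 141 days to 365.25 − 210 = 155 days, i.e. 4.6 to 5.1 months. It is 4.0 months for patients scanned at month 8.
- Section 7.2 says "if a patient is unable to attend on the specified day, assessments may be scheduled for +/- 3 days". That this window covers follow-up CTs is an assumption. With it, any registration-to-treatment gap over 3 days puts every on-time 12-month CT after 12 months from registration. With no gap, about half fall after it.

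**Formula.** Let S be the true PFS curve, d the share of events dated at onset (deaths, and progressions found clinically or on an unscheduled CT), and L the time of the last scheduled CT before the landmark, all from registration. When the 12-month CT falls after the landmark,

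reported PFS(12) = S(12) + (1 − d) × [S(L) − S(12)].

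**Assumed inputs.** Exponential PFS, S(t) = 0.5^(t/median); gap 7 days; section 7.9's month 8 counted from treatment start. Then L = (217 + 7)/30.44 = 7.36 months after a mid-window cycle 8 CT, or 8 + 7/30.44 = 8.23 months after a month 8 CT.

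| Median PFS | Last CT | S(L) | True S(12) | d = 90% | d = 80% | d = 50% |
|---|---|---|---|---|---|---|
| 6 months | cycle 8 | 42.7% | 25.0% | 26.8% | 28.5% | 33.9% |
| 6 months | month 8 | 38.6% | 25.0% | 26.4% | 27.7% | 31.8% |
| 3 months | cycle 8 | 18.3% | 6.25% | 7.5% | 8.7% | 12.3% |
| 3 months | month 8 | 14.9% | 6.25% | 7.1% | 8.0% | 10.6% |

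Example, first row, d = 50%: 25.0 + 0.5 × (42.7 − 25.0) = 33.9%. Simulations of 400,000 patients per case agree to within about 0.2 points.

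**Sensitivity (simulated; median 6 months; d = 80% / 50%).**

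- Gaps of 4 to 21 days: 27–29% / 31–34%.
- Scan window ±14 instead of ±3 days: 27.8 / 31.7% without the month 8 CT, 27.0 / 30.1% with it.
- Falling hazard (Weibull shape 0.6, true 35.0%): 37.0 / 40.4% without, 36.5 / 39.1% with.
- No gap (common origin): 26.9 / 29.8% without, 26.5 / 28.6% with. About half the excess remains, so aligning the origins is not enough.

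**Six-month landmark.** The cycle 6 CT is due by day 168 and 6 months is day 182.6, so the scan precedes the landmark while gap plus dose delay stays under 14.6 days. With a true 50%, the reported value is 50–52% for gaps up to 14 days, and 52% / 55% at 21 days.

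**Thirteen months.** With a 7-day gap the 12-month CT falls at 12.23 months. For median 6, S(12.23) = 24.3% and S(13) = 22.3%. At d = 50%: 22.3 + 0.5 × (24.3 − 22.3) = 23.3%, an excess of about 1 point.

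**Sampling error.** 1.96 × √(0.25 × 0.75/30) = 15.5 points either side of 25%.

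**The case against.** The best counter-argument is that off-schedule detection does most of the work. This is aggressive disease, patients on treatment are examined every cycle, and a CT can be done on concern or at discontinuation. If that finds 90% of events, the excess is 1 to 2 points. The documents give no detection share, so the 80% and 50% cases are no better founded than 90%. This stands, and it is why only a range can be given. It limits the excess but does not remove it.

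The median of 6 months is also generous. Section 1.2.3 cites a median OS of 6.0 months after relapse and 2.5 months in primary refractory disease, although section 1.2.1 gives 6 to 18 months. PFS cannot exceed OS, so the 3-month rows may be closer: about +1, +2 and +4 to +6 points.

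A plotted Kaplan-Meier curve would show the drop just after 12 months, and dating progression when it is documented is common practice. Both are true, but neither changes the landmark value that the plan reports.

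Three stronger readings do not hold:

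- A reader might infer that most enrolled patients are affected. Only those still progression-free and in follow-up near 12 months have this CT, and in these examples they are a minority.
- A reader might take the extreme in which every event waits for a scheduled scan, where 25% would read 39–43%. Deaths and the unscheduled routes rule that out as a realistic case.
- A reader might infer that one or two patients' 12-month CTs fall after the data cut. At 30/24 = 1.25 registrations a month and a gap of 7 to 21 days, 1.3 to 1.9 patients would be due a CT after a cut made one year after the last registration. That ignores earlier progression and death. Scaled by the 6–34% still counted progression-free, it is about 0.1 to 0.6 patients.

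**Conclusion.** The point holds as a minor one. The direction follows from the documents: a registration origin, a later scan clock, and 4.0 to 5.1 months without a scheduled CT before the landmark. Late dating can only raise the 12-month value. How often the CT falls after the landmark depends on a gap the documents do not give: always if the gap exceeds the scan window, and about half the time if there is none.

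The size is conditional on exponential PFS, a 7-day gap, a ±3 day window and an assumed share found off schedule. The tabulated excess is about 1 to 9 points at median 6 months and 1 to 6 points at median 3 months. The median-6 excess is well inside the 15.5-point half-width for 30 patients. A reader might infer that the trial's conclusion on activity is compromised. The documents do not support that: no decision rule uses PFS, and the primary outcome and OS do not depend on this dating. The 6-month PFS is little affected unless gap plus dose delay exceeds about 14 days.

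**What to change.** 1. In section 12.2, keep registration as the origin and keep the planned 12-month estimate, labelled as preceding the 12-month CT.
2. Beside it, report Kaplan-Meier PFS just after the 12-month scan window, for example at 13 months from registration. With a ±3 day window this works for gaps up to 30.4 − 3 = 27 days. State the window that applies to follow-up CTs.
3. Report the observed registration-to-treatment gap, so that readers can judge both landmarks.
4. Time the PFS data cut so that the last patient's 12-month CT is included and the 13-month value is supported. Reconcile the follow-up statements: one year after the end of trial treatment (section 3), at least 12 months from starting treatment for the last patient (section 7.9), a minimum of 12 months with no origin given (section 12.1.2), and analysis one year after the last patient entered (section 12.4).
5. Optional: a Turnbull interval-censored estimate at 12 months as a sensitivity analysis.

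Cost: analysis wording, one extra estimate and a data cut about a month later, with no extra scans. Thirteen months is a less conventional time point, and the added figure will be lower. Part of that drop is real: in the median-6 example true PFS is 25% at 12 months and 22% at 13.

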12.3 Planned Interim Analysis

Accumulating data and analyses will be monitored regularly by the TSC with an independent chair (see section 13.4).

In addition an interim analysis for futility will take place once 15 patients have been recruited and reached the cycle 3 CT scan time point. If the probability of the true response rate being greater than 35% is less than 20% (i.e. observe less than three responses) the TSC would need to make a decision on whether to stop or continue the trial. Both ITT and per protocol analyses will be presented. This stopping rule is provided as guidance only and any decision to stop or continue will be based on a pragmatic assessment of all outcomes.

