12.4 Planned Final Analyses

Final analysis will take place 1 year after the last patient entered the study.

Sample size determinationThe trial will recruit 30 patients with the flexibility to recruit more if required. Given the rare nature of the disease bayesian probability plots for a binary outcome with an uninformative beta prior are used. Given these 30 patients, if the trial observed 11 responses there would be a 60% chance that the true response rate is greater than 35%. Given 13 responses are observed there would be an 84% chance that the true response rate is greater than 35%. See appendix 2 for plots for different scenarios.

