13.4 Trial Safety Committee

A TSC, with an independent chair, will provide overall supervision for the trial and provide advice through its independent chair. The ultimate decision for the continuation of the trial lies with the TSC. The TSC will meet at least 6 months after the first patient has been recruited and every 6 months thereafter during the recruitment and treatment period, to monitor all safety, futility and primary activity data.

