APPENDIX 2 – AVAIL-T BAYESIAN PROBABILITY PLOTS

[figure not shown]
Design

Bayesian probability plot approach using a binary outcome. Uninformative beta prior is used.

For 30 evaluable patients in the trial

1) 11 responses observed

[figure not shown]
We would be greater than 60% sure that the response rate was greater than 35%. The plot below shows the distribution of the responses and the red lines show the 25%, 35% and 45% marks.

P (true response rate > 45%) =	19%
P (true response rate > 35%) =	60%
P (true response rate > 25%) =	94%

2) 12 responses observed

[figure not shown]
We would be greater than 74% sure that the response rate was greater than 35%. The plot below shows the distribution of the responses and the red lines show the 25%, 35% and 45% marks.

P (true response rate > 45%) =	30%
P (true response rate > 35%) =	74%
P (true response rate > 25%) =	97%

3) 13 responses observed

[figure not shown]
We would be greater than 84% sure that the response rate was greater than 35%. The plot below shows the distribution of the responses and the red lines show the 25%, 35% and 45% marks.

$P(\text{true response rate} > 45\%) =$	44%
$P(\text{true response rate} > 35\%) =$	84%
$P(\text{true response rate} > 25\%) =$	98%

4) 16 responses observed:

We would be greater than 98% sure that the true response rate was greater than 35%. The plot below shows the distribution of the responses and the red lines show the 25%, 35% and 45% marks.

[figure not shown]

$P(\text{true response rate} > 45\%) =$	82%
$P(\text{true response rate} > 35\%) =$	98%
$P(\text{true response rate} > 25\%) =$	>99%

For 35 evaluable patients in the trial

1) 13 responses observed:

[figure not shown]
We would be greater than 63% sure that the response rate was greater than 35%. The plot below shows the distribution of the responses and the red lines show the 25%, 35% and 45% response rate marks.

$P(\text{true response rate} > 45\%) =$	18%
$P(\text{true response rate} > 35\%) =$	63%
$P(\text{true response rate} > 25\%) =$	95%

2) 14 responses observed:

[figure not shown]
We would be greater than 75% sure that the response rate was greater than 35%. The plot below shows the distribution of the responses and the red lines show the 25%, 35% and 45% response rate marks.

$P(\text{true response rate} > 45\%) =$	29%
$P(\text{true response rate} > 35\%) =$	75%
$P(\text{true response rate} > 25\%) =$	97%

3) 15 responses observed:

[figure not shown]

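### The two halves of the interim futility rule do not match: with 15 patients, a probability below 20% means three or fewer responses, not fewer than three

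*Combined protocol and SAP*

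**What the plan says.** Section 12.3 states that an "interim analysis for futility will take place once 15 patients have been recruited and reached the cycle 3 CT scan time point". The trigger reads "If the probability of the true response rate being greater than 35% is less than 20% (i.e. observe less than three responses", after which the TSC has to decide whether the trial stops or goes on. The same section adds "Both ITT and per protocol analyses will be presented" and "This stopping rule is provided as guidance only".

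The prior is described only in words. The sample size paragraph in section 12.4 says "bayesian probability plots for a binary outcome with an uninformative beta prior are used", and Appendix 2 repeats this without parameters. Appendix 2 tabulates posterior probabilities for 30 and 35 patients; its text gives none for 15.

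Section 12.2 defines the second analysis set as "a per protocol population of only patients who were eligible and received at least 1 dose of treatment". Section 13.4 has the TSC meet every 6 months "to monitor all safety, futility and primary activity data".

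**The concern.** The bracket in section 12.3 presents the response count as a restatement of the probability. If the two are not equivalent at 15 patients, the sentence contains two thresholds, and some result will trigger a decision under one and not under the other. This is the only numerical interim threshold in the plan. Section 1.1 puts response rates for existing single agents at 20% to 35%, so what matters is how the two forms behave for true rates in that range. If the mismatch is found only once the interim data are in, the choice between the two forms would be made with the response count already known.

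**Working it through.** **Inputs.** Interim n = 15, reference rate 35%, probability cutoff 20% and stated count of fewer than three, all from section 12.3. The prior is an uninformative beta (section 12.4, Appendix 2), parameters not given.

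**Formula.** With a Beta(a, b) prior and r responses in n patients, the posterior is Beta(a + r, b + n − r), and the quantity needed is P(p > 0.35). For a = b = 1 this equals P(Bin(n + 1, 0.35) ≤ r).

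**Step 1: recover the prior from the plan's own figures.** P(p > 0.35) under Beta(1,1):

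| n | Responses | Computed | Appendix 2 |
|---|---|---|---|
| 30 | 11 | 60.3% | 60% |
| 30 | 12 | 73.6% | 74% |
| 30 | 13 | 84.1% | 84% |
| 30 | 16 | 98.1% | 98% |
| 35 | 13 | 62.9% | 63% |
| 35 | 14 | 74.95% | 75% |
| 35 | 15 | 84.46% | 84% |
| 35 | 19 | 99.1% | 99% |

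All eight agree on rounding. The Jeffreys prior gives 58.3% at 11/30 and 83.1% at 13/30, which do not. Beta(1,1) is therefore the prior in use.

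**Step 2: apply it at n = 15.** The posterior is Beta(1 + r, 16 − r), so P(p > 0.35) = P(Bin(16, 0.35) ≤ r).

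| Responses in 15 | P(rate > 35%) | Below 20%? | Fewer than three? |
|---|---|---|---|
| 0 | 0.1% | yes | yes |
| 1 | 1.0% | yes | yes |
| 2 | 4.5% | yes | yes |
| 3 | 13.4% | **yes** | **no** |
| 4 | 28.9% | no | no |

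The 20% criterion is three or fewer. The count in the text corresponds to any probability cutoff above 4.5% and up to 13.4%.

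**Step 3: check that the prior does not drive this.** P(p > 0.35) at 2, 3 and 4 responses in 15:

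- Jeffreys: 3.2%, 10.8%, 25.5%
- Near-Haldane, Beta(0.001, 0.001): 2.1%, 8.4%, 22.1%
- Beta(2,2): 7.8%, 18.9%, 35.5%

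Each puts the 20% cutoff at three or fewer.

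**Step 4: size of the effect.** With X ~ Bin(15, p):

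| True rate | P(X ≤ 2): count form triggers | P(X ≤ 3): probability form triggers | P(X = 3): forms disagree |
|---|---|---|---|
| 10% | 82% | 94% | 13% |
| 20% | 40% | 65% | 25% |
| 25% | 24% | 46% | 22.5% |
| 35% | 6% | 17% | 11% |
| 45% | 1% | 4% | 3% |

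These are chances of prompting a TSC decision, not of stopping the trial.

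**Step 5: other denominators.** Under Beta(1,1), 3 responses give 17.3% at n = 14, 22.1% at n = 13 and 27.8% at n = 12. The 20% cutoff is thus three or fewer at 14, and two or fewer at 13 and 12. The stated count would fit a set of 12 or 13 patients, but section 12.3 specifies 15.

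**The case against.** The arithmetic is not in dispute; the objections concern weight and remedy.

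- **Little hangs on it.** The forms differ at one outcome only. Crossing the line obliges the TSC to decide, not to stop. The rule is guidance, the TSC sees futility and activity data every 6 months, and 3 of 15 would come before it in any case. The sample size, primary outcome and final analysis do not change. All of this stands, and it limits the consequence. It does not make the sentence correct: at 3 of 15, one half of it calls for a decision and the other half does not.
- **The 35% may be the wrong number.** Under Beta(1,1), P(rate > 25%) is 19.7% at 2 of 15 and 40.5% at 3 of 15, so 20% and fewer than three would agree if the reference rate were 25%, a value that Appendix 2 also tabulates. But sections 3, 12.2, 12.3 and 12.4 all use 35%, and nothing in the plan points to 25% for the interim. This is speculation, and the sentence would still need correcting.
- **A 5% cutoff is not unique.** This is right. 5% is one of many values that match fewer than three at n = 15, and it behaves differently elsewhere: 2 of 14 gives 6.2%, which would not trigger.

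**Conclusion.** The point holds. At the stated 15 patients and 35% reference rate, a posterior probability below 20% means three or fewer responses, and the count given in section 12.3 is one too low for it. The result rests on a Beta(1,1) prior, inferred from Appendix 2 rather than stated, but the cutoff is the same under the other three priors in step 3. The practical effect is on when the TSC is prompted to decide: 25 percentage points more often under the probability form at a true rate of 20% (65% against 40%), and 11 points more often at 35% (17% against 6%). The plan does not show which form was intended. Because this is a numerical decision threshold that is wrong as written and takes one sentence to put right, it should be corrected before the interim.

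**What to change.** The sponsor should choose one of two consistent wordings for section 12.3 before the interim data are seen:

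- keep the 20% and change the count to three or fewer responses in 15; or
- keep fewer than three responses in 15 and change the probability to one that matches, for example less than 5%.

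Two secondary additions are worth making in the same edit. State the prior as Beta(1,1). State also that the probability governs and the count is recomputed when the number analysed is not 15, since a per-protocol analysis is presented as well. If the second wording is chosen, the probability should be picked with those smaller denominators in mind.

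The cost is one sentence and a few lines of code. The choice itself has a price. The 20% version prompts review more often when the drug is as active as the reference rate (17% rather than 6% at 35%). The count version prompts it less often when the drug is weak (40% rather than 65% at 20%).
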